## 6.2. Exclusion Criteria

Subjects will be excluded from study enrollment if they meet any of the following criteria at screening and/or enrollment:

- [8] are investigative site personnel directly affiliated with this study and their immediate families. Immediate family is defined as a spouse, biological or legal guardian, child, or sibling
- [9] are Lilly employees or employees of Covance

- [10] are currently enrolled in a clinical study involving an investigational product (IP) or any other type of medical research judged not to be scientifically or medically compatible with this study
- [11] have participated in a clinical trial involving an IP within 30 days or 5 half-lives (whichever is longer) prior to screening. If the clinical trial involved treatment with biologic agents (such as monoclonal antibodies, including marketed drugs), at least 3 months or 5 half-lives (whichever is longer) should have elapsed prior to Day 1
- [12] have previously completed or withdrawn from this study or any other study investigating LY3074828, and have previously received the IP
- [13] have known allergies to LY3074828, related compounds, or any components of the formulation, or history of significant atopy
- [14] have an abnormality in the 12-lead ECG that, in the opinion of the investigator, increases the risks associated with participating in the study
- [15] have an abnormal blood pressure as determined by the investigator
- [16] have a history or presence of cardiovascular, respiratory, hepatic, renal, gastrointestinal, endocrine, hematological, or neurological disorders capable of significantly altering the absorption, metabolism, or elimination of drugs; of constituting a risk when taking the IP; or of interfering with the interpretation of data
- [17] have known or ongoing psychiatric disorders deemed clinically significant by the investigator
- [18] regularly use known drugs of abuse and/or show positive findings on drug screening
- [19] show evidence of HIV infection and/or positive HIV antibodies
- [20] show evidence of hepatitis C and/or positive hepatitis C antibody
- [21] show evidence of hepatitis B, and/or positive hepatitis B surface antigen, and/or hepatitis B core antibody
- [22] are women who are lactating
- [23] have used or intend to use over-the-counter or prescription medications, including herbal medications, within 14 days prior to dosing and for the duration of the study. Stable doses of oral contraceptive or hormone-replacement therapy are permitted, at the discretion of the investigator
- [24] have donated blood of more than 500 mL within 1 month prior to screening

- [25] have an average weekly alcohol intake that exceeds 21 units per week (males) and 14 units per week (females), have a positive test for ethanol, or are unwilling to abide by the alcohol restrictions described in Section 6.3.2 (1 unit = 12 oz or 360 mL of beer; 5 oz or 150 mL of wine; 1.5 oz or 45 mL of distilled spirits)
- [26] have a tobacco consumption of more than 10 cigarettes per day (or equivalent), are unwilling to refrain from smoking for approximately 1 hour prior to each ECG and vital sign measurements during the study, or who are unwilling to abide by the CRU smoking guidelines described in Section 6.3.2
- [27] have had symptomatic herpes zoster within 3 months of screening
- [28] show evidence of active or latent TB, as documented by medical history, examination, and TB testing (negative [not indeterminate] QuantiFERON® -TB Gold test); or have had household contact with a person with active TB, unless appropriate and documented prophylaxis treatment has been given. Subjects with any history of active TB are excluded from the study, regardless of previous or current TB treatments
- [29] have received live vaccine(s), including attenuated live vaccines and those administered intranasally, within 8 weeks of screening, or intend to during the study
- [30] have been treated with steroids within 1 month of screening, or intend to during the study
- [31] are immunocompromised
- [32] have received treatment with biologic agents (such as monoclonal antibodies) for a medical condition within 3 months or 5 half-lives (whichever is longer) prior to Day 1
- [33] have significant allergies to humanized monoclonal antibodies
- [34] have clinically significant multiple or severe drug allergies, or intolerance to topical corticosteroids, or severe posttreatment hypersensitivity reactions (including, but not limited to, erythema multiforme major, linear immunoglobulin A dermatosis, toxic epidermal necrolysis, or exfoliative dermatitis)
- [35] have had lymphoma, leukemia, or any malignancy within the past 5 years except for basal cell or squamous epithelial carcinomas of the skin that have been resected with no evidence of metastatic disease for 3 years
- [36] have had breast cancer within the past 10 years
- [37] have excessive tattoos over the abdomen that would interfere with injection-site assessments

[38] in the opinion of the investigator, are unsuitable for inclusion in the study

### **6.3. Lifestyle and/or Dietary Requirements**

Throughout the study, subjects may undergo medical assessments and review of compliance with requirements before continuing in the study.

#### **6.3.1. Meals and Dietary Restrictions**

Subjects will fast overnight for at least 8 hours before dosing (water is permitted). Standard meals will be provided at all other times while subjects are resident at the CRU, as per the CRU's policy.

#### **6.3.2. Caffeine, Alcohol, and Tobacco**

Subjects will not consume caffeinated beverages (decaffeinated beverages are permitted) while at the CRU, and for 12 hours prior to admission to the CRU. At other times during the outpatient period, subjects will be allowed to maintain their regular caffeine consumption.

Alcohol consumption is not permitted while at the CRU, and for 12 hours prior to each study visit. At other times, alcohol consumption should be limited to 2 units per day (1 unit = 12 oz or 360 mL of beer; 5 oz or 150 mL of wine; 1.5 oz or 45 mL of distilled spirits).

Subjects who smoke will be advised to not increase their consumption of tobacco products during the study. Subjects will be asked to refrain from smoking for approximately 1 hour prior to each ECG and vital sign measurements, and to abide by the CRU smoking guidelines.

#### **6.3.3. Activity**

Subjects will be advised to maintain their regular levels of physical activity/exercise during the study, but to refrain from strenuous activity from 24 hours prior to each visit and 48 hours prior to any visit where creatine phosphokinase testing will occur (Day -1, Day 8, and Day 29 in Part A, and Day -1, Day 15, and Day 43 in Part B). While certain study procedures are in progress at the site, subjects may be required to remain recumbent or sitting.

#### **6.3.4. Blood and Plasma Donation**

Subjects will not donate blood or plasma for 12 weeks following dosing with the study drug.

### **6.4. Screen Failures**

Individuals who do not meet the criteria for participation in this study (screen failure) may not be re-screened.

## 7. Dosing Regimens

### 7.1. Dosing Regimens Administered

This study evaluates the PK, safety, and tolerability of, and pain associated with, LY3074828 solution formulation SC dose administered by investigational site staff using 2 x 1-mL and 1 x 2-mL PFS injections (Part A); and compares the safety and tolerability of, and pain associated with, 1 x 1-mL and 1 x 2-mL AI injections self-administered with 2 different injection speeds (Part B).

Using the investigational 2-mL AI, the targeted injection duration will be approximately 13 seconds for slow injection rate and approximately 5 seconds for fast injection rate. Using the investigational 1-mL AI, the targeted injection duration will be approximately 7 seconds for slow injection rate and approximately 4.5 seconds for fast injection rate. Manual injections using the investigational PFS should target an injection duration of about 5 to 10 seconds for 1-mL PFS for each injection and about 5 to 15 seconds for 2-mL PFS, to approximate the injection time range for AIs. Approximate injection durations for AIs and PFSs will be obtained using a calibrated stopwatch and recorded in the electronic case report form (eCRF).

Drug and device accountability records will be maintained by the site pharmacy.

[Table AMAQ.2](#) and [Table AMAQ.3](#) show the dosing regimens for Part A and Part B, respectively.

**Table AMAQ.2. Dosing Regimens Administered – Part A**

Dosing Regimen	PFS (250 mg)	PFS (250 mg)
Reference/test	Reference	Test 1
Product	LY3074828	LY3074828
Dose	250 mg	250 mg
Concentration	125 mg/mL	125 mg/mL
Injection volumes	2 × 1 mL (2 mL total)	1 × 2 mL (2 mL total)
Number of injections	2	1
Injection rate	5 to 10 seconds	5 to 15 seconds
Formulation and presentation	Solution in a PFS	Solution in a PFS

Abbreviations: PFS = pre-filled syringe.

**Table AMAQ.3. Dosing Regimens Administered – Part B**

Dosing Regimen	2-mL AI (250 mg)	1-mL AI (125 mg)
Reference/test	Test 2 and Test 3	Test 4 and Test 5
Product	LY3074828	LY3074828
Dose	250 mg	125 mg
Concentration	125 mg/mL	125 mg/mL
Injection volumes	1 × 2 mL (2 mL total)	1 × 1 mL (1 mL total)
Number of injections	1	1
Injection rate	Approximately 13 seconds (Test 2) Approximately 5 seconds (Test 3)	Approximately 7 seconds (Test 4) Approximately 4.5 seconds (Test 5)
Formulation and presentation	Solution in an AI	Solution in an AI

Abbreviations: AI = autoinjector.

Investigational AIs will be assembled at the site by Lilly Delivery and Device Research and Development engineers. Device Development Quality Assurance will inspect the assembled investigational devices on site to ensure basic good manufacturing practice (GMP) guidelines are met, and that assembly is performed as per GMP procedures, prior to use in the clinical trial. The investigational PFSs containing LY3074828 will be supplied by Lilly fully assembled.

Adjustments to the device (such as changing the spring) will be based on injection duration and tolerability/AEs (pain, bleeding, bruising, leakage, induration, swelling, pruritus, and erythema/redness), and will be performed on site. Device issues that result in AEs will be reported as product quality complaints (PCs).

All injections, whether administered by PFS or AI, will be given into the lower quadrant of the abdomen, with site staff or subject selecting left or right quadrant when a single injection is being given. For administrations requiring 2 injections, injections will be given into separate lower quadrants (right and left). Investigational product administered using PFS will be administered to subjects on-site by designated trained clinical site personnel. Investigational product administered using AI will be self-administered by subjects on-site after receiving instruction from trained clinical site personnel.

Further information regarding SC administration will be included in the device Instructions for Use (IFU) for the PFS and in the device IB (which contains IFU) for the AI.

In some cases, the site may destroy the material if, during the investigative site selection, the evaluator has verified and documented that the site has appropriate facilities and written procedures to dispose of clinical trial materials.

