#### Part B

- Tests 2 and 3: 250 mg LY3074828 solution formulation, 1 x 2-mL 125-mg/mL AI slow injection (Test 2; targeting approximately 13-second injection time) and fast injection (Test 3; targeting approximately 5-second injection time) using an investigational 2-mL AI
- Tests 4 and 5: 125 mg LY3074828 solution formulation, 1 x 1-mL 125 mg/mL AI slow injection (Test 4; targeting approximately 7-second injection time) and fast injection (Test 5; targeting approximately 4.5-second injection time) using an investigational 1-mL AI

For Part A, subjects will report to the clinical research unit (CRU) on Day -1 and will remain at the CRU until the scheduled procedures have been completed on Day 2. After randomization to either a 2 x 1-mL or a 1 x 2-mL 125-mg/mL PFS dose regimen, study drug will be administered by investigative site staff by SC injection in the abdomen in the morning of Day 1 after an overnight fast.

For Part B, subjects will report to the CRU on Day -1 and will remain at the CRU until the scheduled procedures have been completed on Day 3. Subjects will be randomized to receive, on Days 1 and 2, either a 1 x 1-mL or a 1 x 2-mL 125-mg/mL AI dose regimen. The allocated

AI dose regimen will be self-administered by slow and fast SC injection(s) on consecutive days (sequence randomized) in the abdomen after an overnight fast.

**Outpatient Follow-up Period (12 weeks):** The follow-up period will include outpatient visits for a total of 12 weeks (Days 4, 8, 11, 15, 22, 29, 43, 57, 71, and 85 for Part A; Days 15, 43, and 86 for Part B) following dose administration on Day 1 to assess the PK, safety, and tolerability of, and pain associated with, LY3074828 PFS administrations for Part A, and to assess the safety and tolerability of, and pain associated with, LY3074828 investigational AI administrations for Part B.

Safety and tolerability will be explored by clinical laboratory tests, vital sign measurements, 12-lead ECGs, recording of AEs and product complaints, physical examinations/medical assessments, immunogenicity, and injection-site assessments. Pain assessments will be made using the Short Form McGill Pain Questionnaire (SF-MPQ), which includes a subject-assessed injection-site pain visual analog scale (VAS).

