## 5.2. Number of Participants

A total of approximately 72 subjects (approximately 36 subjects per study Parts A and B) who fulfill the eligibility criteria will be randomized to 1 of 2 dosing regimen arms within their assigned study part, with 18 subjects randomized to each arm in order to ensure completion of 16 subjects in each. A subject's study participation is considered as complete if he/she receives the study drug as per the protocol requirements and completes all activities up to and including at least Day 57 for Part A or up to and including at least Day 15 for Part B. A maximum of 4 subjects per arm per study part may be replaced if multiple subjects do not complete the study.

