## 5.4. Scientific Rationale for Study Design

Conducting the study in healthy subjects mitigates the potential confounding effects of the disease state and concomitant medications in patients. Healthy subjects are frequently used in the assessment of bioavailability of both small and large molecules.

For Part A, single doses of LY3074828 and the PK sampling time points have been selected to generate PK profiles sufficient to fulfill the study objectives. As the primary endpoints for Part A of this study are PK-related and are not subject to bias, it is not considered necessary for this study to be blinded. Subjects and site staff will be aware of the administration route and treatment.

For Part B, only an evaluation of safety and tolerability of, and pain associated with, the investigational AI administrations is intended. Pharmacokinetic samples are collected only in conjunction with immunogenicity samples to provide concentrations of LY3074828 to aid in the interpretation of ADA data if needed.

For Part A, a parallel-group design was chosen because a crossover design is impractical for compounds that have long half-lives, such as monoclonal antibodies. Additionally, a crossover study design could confound PK data if subjects develop neutralizing ADAs.

For Part B, a crossover design was chosen as PK analysis is not an endpoint and a relatively short time between injections will allow a more accurate comparison of injection-site pain by subjects

Monoclonal antibody therapy has been associated with hypersensitivity reactions, including injection-site reactions. Follow-up details on injection-site reactions will be collected by the investigative site regarding the severity, duration, type, and timing of the start of the event in relation to the start of study drug administration in order to further characterize these events.

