## **7.2. Method of Treatment Assignment**

Subjects will be randomized within 1 study part (Part A or Part B) to 1 of 2 dosing regimen arms ([Table AMAQ.2](#) and [Table AMAQ.3](#)). In addition, the sequence of injections on Days 1 and 2 (fast/slow versus slow/fast) for subjects participating in Part B will be randomized.

Randomization will be performed using a computer-generated randomization schedule.

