#### **10.3.1.2. Statistical Evaluation of Safety**

##### **10.3.1.2.1. *Injection-site Pain***

For Parts A and B, the intensity of pain at each injection site immediately (approximately within 5 minutes) following the start of the injection will be evaluated, as reported by the subject and measured according to the 0 to 100 mm VAS that forms part of the SF-MPQ. Assessments will also be performed at 15, 30, 60, 120, and 240 minutes post injection; however, the primary endpoint will be the 0-hour assessment.

Descriptive statistics will be used to summarize the intensity and type of pain at each time point as captured by the SF-MPQ.

In Part A, a linear fixed-effects model will be used to analyze the 0-hour (post-injection) pain VAS score and SF-MPQ total score. The model will include treatment (Reference or Test 1) as a fixed effect. The least squares (LS) means and differences in LS means (between Test 1 and Reference) will be presented along with the corresponding 90% CI. The distribution of the data will be explored prior to analysis to determine whether data transformation is required. It is possible that the pain scores will be 0 so if the distribution of the data implies that a log-transformation is required then the score may be updated to  $\log(VAS+1)$  to allow for the inclusion of the 0 values in the analysis.

A similar model will be used to analyze the 0-hour (post-injection) pain VAS score and SF-MPQ total score in Part B.

The following comparisons will be performed in Part B:

- Test 2 versus Test 3 (slow versus fast injection for 2-mL AI)
- Test 4 versus Test 5 (slow versus fast injection for 1-mL AI)

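### Part B leaves the injection quadrant to free choice on each day, so same-side local carry-over that differs by speed could bias the slow-versus-fast pain contrast by an unknown amount in either direction

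*Protocol*

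**What the plan says.** Protocol Section 5.1 describes the Part B regimen as "self-administered by slow and fast SC injection(s) on consecutive days (sequence randomized". Table AMAQ.3 counts each administration as one injection.

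The text after that table places all injections in a lower abdominal quadrant, "with site staff or subject selecting left or right quadrant when a single injection is being given". The next sentence restricts placement in one case only: "For administrations requiring 2 injections, injections will be given into separate lower quadrants (right and left". That case is the Part A Reference arm. Part B, with one injection per day, falls under the free-choice rule.

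Section 5.4 justifies the crossover on the ground that "a relatively short time between injections will allow a more accurate comparison of injection-site pain by subjects". It does not discuss local carry-over. Section 7.2 says that "the sequence of injections on Days 1 and 2 (fast/slow versus slow/fast) for subjects participating in Part B will be randomized". It gives no allocation ratio or blocking and does not randomize the side.

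For pain, Section 10.3.1.2.1 states that "the primary endpoint will be the 0-hour assessment". The Part B model is described there and in SAP Section 9.4.8 only as similar to the Part A model, whose one named effect is treatment. No period, sequence, subject or side term is named.

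**The concern.** Part B is a two-period crossover with about a day between periods, and pain is one of its primary endpoints. Slow versus fast, within each device, is the only kind of Part B comparison listed. If the second injection lands near a site that is still tender, the Day 2 score may contain pain that belongs to the Day 1 injection.

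Two routes could make this depend on speed. Residual tenderness may differ between slow and fast injections. Separately, the chance of reusing the quadrant may differ, because a subject who found Day 1 painful can change sides while one who did not can stay. Keeping subjects unaware of the speed (Section 7.3) does not close the second route, since the subject knows how Day 1 felt.

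The protocol already separates quadrants where two injections belong to one administration. It does not do so where two injections a day apart are compared with each other.

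**Working it through.** **Inputs from the documents.** Each Part B arm is planned "with 18 subjects randomized to each arm in order to ensure completion of 16 subjects in each" (Protocol Section 5.2). Each subject has one slow and one fast injection about 24 hours apart, in randomized order. The documents give no residual pain, reuse rate, pain SD or target difference for Part B. There is thus no figure of the plan's own to reproduce; the 0.28 log-scale precision in Section 10.1 concerns Part A pharmacokinetics.

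**Notation (all values assumed).**
- p_S, p_F: probability of reusing the Day 1 quadrant after a slow or a fast first injection.
- c_S, c_F: mean pain (mm VAS) added to the Day 2 score among those who reuse it.
- π: any common Day 2 effect.
- n_SF, n_FS: subjects in the slow/fast and fast/slow sequences.

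**Derivation, slow minus fast.**
- Slow/fast: the fast score is taken on Day 2, so the expected difference is true − π − p_S·c_S.
- Fast/slow: the slow score is taken on Day 2, so the expected difference is true + π + p_F·c_F.
- Over all subjects: bias = [n_FS(π + p_F·c_F) − n_SF(π + p_S·c_S)] / (n_SF + n_FS).
- With balanced sequences, or with period in the model: **bias = (p_F·c_F − p_S·c_S)/2**.

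If fast injections truly hurt more, slow minus fast is negative. A positive bias then shrinks the difference and a negative bias enlarges it.

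**Results.**

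1. *Equal residual pain and equal reuse, sequences 9:9 or 8:8.* Bias = 0.

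2. *Residual pain larger after fast by d, same reuse p for both speeds.* Bias = p·d/2.

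| d (mm, assumed) | p = 0.5 | p = 1 |
|---|---|---|
| 2 | 0.5 | 1 |
| 4 | 1 | 2 |
| 6 | 1.5 | 3 |

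A period term does not remove this.

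3. *Equal residual pain, sore side avoided after fast.* With 5 mm and reuse of 50% after slow and 25% after fast: (0.25×5 − 0.50×5)/2 = −0.625 mm. With 10 mm and reuse of 50% and 0%: (0 − 0.50×10)/2 = −2.5 mm. The sign is opposite to case 2.

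4. *Equal residual pain of 10 mm, full reuse, unbalanced sequences, no period term (π set to 0).* At 8 slow/fast and 10 fast/slow: 10×(10 − 8)/18 = 1.11 mm. At 6 and 12: 10×(12 − 6)/18 = 3.33 mm. Both become 0 once period is modelled. If the sequence were assigned by simple 1:1 randomization, which the protocol neither states nor rules out, the two groups would differ by 4 or more with probability 48% at n = 18.

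5. *Opposite quadrants on the two days.* p_S = p_F = 0, so the same-quadrant term is 0 in every case above.

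Simulation (20,000 runs per scenario) agreed with the formula: −0.04 against 0 (equal 5 mm, 50% reuse, 9:9), 2.49 against 2.5 (0 mm after slow and 10 mm after fast, 50% reuse, 9:9), and 3.34 against 3.33 (the 6:12 case).

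**The case against.** Several points weigh on the other side.

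**The instructions are elsewhere.** Section 7.1 refers to the device Instructions for Use and device Investigator's Brochure for administration details, and Section 9.4.4.2 has injections follow sponsor instructions. A site-rotation rule could sit there. This stands as a limit: silence in the protocol does not prove that no rule exists. But the protocol itself grants free choice, so any such rule would need to be reconciled with it. Likewise, the eCRF is not supplied, so the side may already be recorded.

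**Safeguards exist.** Sites are marked so that they can be found again, staff watch each self-injection, subjects are not told the speed, and the sequence is randomized. These help, but none prevents reuse of the quadrant, and randomization handles only carry-over that is equal for both speeds.

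**Tenderness at 24 hours is not shown.** A reader might infer it because the Part B schedule assesses the Day 1 site at 24 hours. The documents do not support that: the same site is assessed again at Day 15, so a scheduled check is not evidence of symptoms. Scheduled pain scoring stops at 240 minutes, and 24 hours is six times that. Nor do the documents show that residual tenderness would raise a rating of new injection pain taken within about 5 minutes.

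**Direction.** A reader might also infer that the bias must run toward no difference, because fast injections would leave more tenderness. That does not follow. If sore subjects change sides, reuse after fast injections falls and the sign can reverse (case 3).

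**Consequence.** The plan states no margin or threshold for Part B pain that a bias of 1 mm would cross. This stands, and it limits the priority of the point.

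**Conclusion.** The gap is real on the protocol's text: nothing in it stops the Day 2 injection from going into the Day 1 quadrant, and the choice may respond to the Day 1 experience. Sequence randomization does not protect the contrast against residual pain or reuse that differs by speed, and a period term would not do so either.

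The size cannot be determined from the documents. The 0.5 to 1.5 mm (50% reuse) and 1 to 3 mm (full reuse) follow only from an assumed 2 to 6 mm difference in residual pain. They are not estimates of what will happen. The bias may be zero, and its sign may be either.

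This is therefore a cheap improvement to the design of a primary-endpoint comparison. It is not a demonstrated bias, and it does not make the Part B pain results unusable.

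**What to change.** In Protocol Section 7.1, extend the separate-quadrant rule to Part B: opposite lower quadrants on Days 1 and 2. Take the side order (left then right, or right then left) from the randomization schedule, with a documented exception where a side is unsuitable. Record the side in the eCRF if it is not already captured. Check the device Instructions for Use and device Investigator's Brochure for site-rotation wording and reconcile it with Section 7.1.

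The cost is one sentence, one column in the randomization list and, at most, one eCRF field. Dose, timing and device are unchanged. The downside is that subjects and staff lose the free choice of side. The change removes same-quadrant carry-over only; a general Day 2 effect remains a matter for sequence balance and the model.
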